**Centering equity in FDA regulation: Front-of-package
food label effects in Latiné and limited English
proficiency populations**

NCT number NCT06293963

Document Date 07/26/2024

Study Protocol and Analytic Plan

Title: Centering equity in FDA regulation: Front-of-package food label effects in Latiné and limited English proficiency populations

NCT #: NCT06293963

Introduction

This study aims to determine the front-of-package label design that is most effective at helping Latiné consumers identify healthier products and to explore whether the benefits of front-of-package label design differ by English proficiency. This document pre-specifies our planned analytic approach prior to data collection.

Study Protocol

Participants will complete an online randomized experiment programmed in Qualtrics. After providing informed consent, participants will be randomly assigned to view 1 of 4 types of front-of-package nutrient labels: numerical label, interpretive text-only label, interpretive label containing a magnifying glass icon, or separated interpretive labels containing a magnifying glass icon. Participants will view 3 sets of similar products (with 3 products per set) displaying their assigned label type and will answer selection questions about the products. These selection questions will be repeated 3 times, once for each food product. The survey will also ask questions about reactions to the labels and demographics in the online survey.

Hypotheses

Correct identification of healthiest product (co-primary outcome): We predict that correct identification of the healthiest product will be highest for participants assigned to the separated interpretive magnifying glass icon label, followed by the interpretive magnifying glass icon label, the interpretive text-only label, and the numerical label (H1).

Correct identification of least healthy product (co-primary outcome): We predict that correct identification of the least healthy product will be highest for participants assigned to the separated interpretive magnifying glass icon label, followed by the interpretive magnifying glass icon label, the interpretive text-only label, and the numerical label (H2).

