Correct identification of products high in nutrients (secondary outcome): We predict that correct identification of which products are high in nutrients of concern will be highest for participants assigned to the separated interpretive magnifying glass icon label, followed by the interpretive magnifying glass icon label, the interpretive text-only label, and the numerical label (H3).

Selection of healthiest product for purchase (secondary outcome): We predict selection of the healthiest product will be highest for participants assigned to the separated interpretive magnifying glass icon label, followed by the interpretive magnifying glass icon label, the interpretive text-only label, and the numerical label (H4).

Main Analyses

We will use a two-sided critical alpha of 0.05 to conduct all statistical tests. All confidence intervals presented will use a 95% confidence level. Analyses of the primary and secondary outcomes will include all participants according to the trial arm to which they were randomized.

For all of the selection tasks, participants will have a time limit to simulate real-world conditions where people make shopping decisions quickly. We will recode missing data as “no” or “incorrect” for all 4 selection outcomes. The healthiest product is defined as the one that is high in the fewest number of nutrients of concern (i.e., only 1 nutrient). The least healthy product is defined as the one that is high in the highest number of nutrients of concern (i.e., 3 nutrients). Correct identification of products high in nutrients is defined as identifying the products having 20% or more of the daily value of the nutrient or labeled with “high in,” per FDA’s guidance around “high” levels of nutrients of concern. The responses to these three correct identification tasks will be dichotomized as correct vs. incorrect. For the selection outcome, we will dichotomize the outcome to selection of the healthiest product vs. selection of either of the other two products.

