We will descriptively report unadjusted means for the primary and secondary outcomes for each experimental arm. To test H1-H4, analyses will use mixed effects logistic regression models to examine the impact of label arm on the outcomes, accounting for repeated measures within participants. Models will regress the outcome on indicator variables for the labeling arm (excluding the numerical label as the referent) and indicator variables for product category, treating the intercept as random. Analyses will calculate average differential effects for each interpretative label compared to the numerical label, representing the differences in predicted probabilities by label type. We will also compare each interpretive label to each other. We will not adjust the p-value for each label type compared to the numerical label. We will adjust for multiple tests for the three additional pairwise comparisons (within each family of outcomes) among interpretive labels using a Bonferroni-Holm correction.

Exploratory Analyses

In exploratory analyses, we plan to report the impact of label type on the primary and secondary outcomes when stratifying by product type.

To examine whether the impacts of front-of-package label design on the co-primary outcomes differ by English proficiency, we will regress outcomes on label type, product type, English proficiency (high vs. limited), and the interaction between label type and English proficiency. These analyses will use linear probability models (rather than logistic regression) to aid in interpretation, as recommended for examining moderation for binary outcomes. We will use the same approach to determine whether the impacts of front-of-package label design differs by parental status.

Additionally, the survey will display 4 types of icon labels in random order, asking participants which label best signals when foods are high in sodium, saturated fat, and added sugars and which label most discourages purchasing of foods high in these nutrients. To assess which icon designs are most promising for front-of-package nutrition labels, we will calculate the proportion of participants who selected each label as best signaling when foods are high in sodium, saturated fat, and added sugars and the proportion who selected each label as most discouraging of purchasing foods high in these nutrients.

Sample Size and Power

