We used G*Power 3 to estimate sample size needs. To be conservative, we powered the study to detect a difference in the co-primary outcomes between the 2 label designs that we anticipate will be most similar (i.e., the interpretative magnifying glass icon and interpretative text-only label). Power analyses assumed 55% of participants in the interpretative magnifying glass icon

condition would correctly identify the least healthy and healthiest products (based on a prior study using similar methods) and a two-tailed critical alpha of 0.017 (0.05 divided by 3 to correct for multiple comparisons). Under these assumptions, a sample of 1,000 per condition (4,000 total) yields 80% power to detect effects of $OR=1.16$ or larger between any 2 label designs for each primary outcome. This is a conservative estimate of effect size based on prior studies showing effect sizes of 1.10–1.80 between similar labels. This would be considered a small effect size, equivalent to Cohen's $d=0.08$.

Interim Analysis

No interim analyses are planned.

Exclusions and Outliers

We will exclude participants who complete the survey implausibly quickly (defined as <1/3 of the median completion time). We will exclude participants who complete less than 90% of the survey.

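### The exploratory label effects by product type come with no test of whether they differ between products, although the plan specifies such a test for its other two moderators.

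*Combined protocol and SAP*

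**What the plan says.** Exploratory Analyses opens with a plan to "report the impact of label type on the primary and secondary outcomes when stratifying by product type". The section gives no model for this analysis, no test of heterogeneity between products, and no correction or rule for comparing products.

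The Main Analyses model includes "indicator variables for product category, treating the intercept as random". Product therefore enters as a main effect only, and no label-by-product term appears anywhere in the plan.

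The next paragraph of Exploratory Analyses handles moderation differently. For the co-primary outcomes it fits a linear probability model containing "the interaction between label type and English proficiency", and then adds: "We will use the same approach to determine whether the impacts of front-of-package label design differs by parental status".

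On the design, the Study Protocol section says: "These selection questions will be repeated 3 times, once for each food product". Each participant thus contributes to all three products. On the significance level, Main Analyses says: "We will use a two-sided critical alpha of 0.05 to conduct all statistical tests".

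**The concern.** Results shown by product invite the question of whether a label works better for some foods than for others. The plan offers only separate sets of estimates to answer it. A label significant in two products and not in the third looks like a product difference, yet it can easily arise from sampling error around one common effect. The difference between a significant and a non-significant result is not itself a test.

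At stake is the interpretation of an exploratory table. A chance pattern could be read as evidence that a label design suits some product categories and not others. The plan already uses the appropriate tool for two other moderators, so the omission is easy to repair.

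**Working it through.** **Inputs from the documents.** Sample Size and Power gives 1,000 per condition, a 55% reference rate, a target odds ratio (OR) of 1.16, and prior effects of 1.10 to 1.80. There are three products, each seen by every participant. Alpha is 0.05 two-sided for all tests; the power calculation uses a "two-tailed critical alpha of 0.017 (0.05 divided by 3 to correct for multiple comparisons").

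**Assumptions.** The documents give no within-person correlation between products, so I use 0, 0.3 and 0.5. I take 55% as the reference rate in every product, one yes/no response per participant per product, and no correction across products.

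**The plan's own figure.** The plan states 80% power at OR 1.16. The equivalence to d = 0.08 reproduces: ln(1.16) × √3/π = 0.082. The 80% does not reproduce for a two-label comparison of proportions at alpha 0.017. I get 23% with 1,000 responses per arm and 68% with 3,000 per arm treated as independent. The G*Power test family and the correlation are not stated, so I take this no further. Nothing below depends on the 80%.

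**Step 1: power within one product.** With OR 1.16 downward from 55%, the odds are (0.55/0.45)/1.16 = 1.0536, so p₂ = 0.5131 and the difference is 0.0369. The pooled proportion is 0.5315.
- Standard error under the null: √(2 × 0.5315 × 0.4685/1000) = 0.02232.
- Standard error under the alternative: √((0.55 × 0.45 + 0.5131 × 0.4869)/1000) = 0.02230.
- Power = Φ((0.0369 − 1.96 × 0.02232)/0.02230) = Φ(−0.305) ≈ 38%.

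**Step 2: chance of a mixed pattern under an identical true effect.** If the three products were independent, P(some but not all significant) = 1 − π³ − (1 − π)³, where π is the per-product power. With π = 0.38 this is 1 − 0.055 − 0.238 = 0.707. For positive correlation, the three z-statistics are treated as trivariate normal with a common mean and pairwise correlation equal to the within-person correlation, since the same people supply all three.

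| True OR (same in all products) | Power per product | Mixed, corr. 0 | corr. 0.3 | corr. 0.5 |
|---|---|---|---|---|
| 1.00 | 5% | 14% | 14% | 12% |
| 1.10 | 19% | 45% | 38% | 32% |
| 1.16 | 38% | 71% | 57% | 48% |
| 1.30 | 83% | 42% | 35% | 30% |
| 1.50 | 99.5% | 1.5% | 1.5% | 1.4% |
| 1.80 | about 100% | about 0% | about 0% | about 0% |

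**Step 3: sensitivity to alpha.** At 0.017 in place of 0.05, the mixed-pattern probability is 53%, 44% and 37% at OR 1.16, and 62%, 51% and 43% at OR 1.30. A stricter level does not remove the problem.

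**Step 4: what a test would offer.** Four labels and three products give (4 − 1) × (3 − 1) = 6 degrees of freedom per outcome. Tested at 5%, false statements of heterogeneity are held to about 5% per outcome. For power, take a contrast of one label pair between two products, with 55% in both arms. The label difference within a product has standard error √(2 × 0.55 × 0.45/1000) = 0.02225. The difference between two products has standard error 0.02225 × √(2(1 − ρ)) = 0.0315, 0.0263 and 0.0222. Multiplying by 1.96 + 0.84 gives differences detectable with 80% power of 8.8, 7.4 and 6.2 percentage points.

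**The case against.** The strongest reply is that the plan promises only to report these effects. It states no hypothesis about product differences, labels the analysis exploratory, and keeps its moderation wording for English proficiency and parental status. That is a fair reading, and it is why the point is minor. A reader might infer that the plan intends to claim product differences from separate p-values; the text does not say so.

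A reader might also infer that the random-intercept model will fail within products, because each person then gives a single response for most outcomes. The documents do not support that either. The mixed model is specified for H1–H4, nothing says it will be refitted by product, and ordinary logistic regression would serve.

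Nor should the product-specific estimates be discarded as inefficient. Missing responses are recoded as incorrect, so every analysed participant contributes to all three products, and label arm is the only regressor left within a product. A joint model therefore adds essentially nothing to those estimates. Within-person information matters for the comparison between products.

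Scale is a further valid objection. The plan reports differences in predicted probability. With a common OR of 1.5 and assumed baselines of 30%, 55% and 80%, those differences are 9.1, 9.7 and 5.7 points. A log-odds interaction would be zero while effects on the reported scale differ. The test should therefore be on the probability scale.

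Finally, adding a test leaves the mixed significance pattern visible, and the test has limited power. Both are true. The test still gives a valid basis for a statement about differences, which separate p-values do not.

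**Conclusion.** The point holds as a small gap in an exploratory analysis. Near the plan's own target effect, a split in significance between products is about as likely as not, or more so, even when the label works identically in all three: 48% to 71% at OR 1.16. It is 30% to 42% at OR 1.30 and negligible from OR 1.5 upward. Much of the plan's cited range of prior effects is therefore not exposed.

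These figures describe one label contrast on one outcome. They should not be read as applying uniformly to every pair and outcome: effects will vary between contrasts, and the plan does not commit to reporting all six pairs by product. They also rest on the assumed correlations, a 55% rate in every product and an uncorrected alpha of 0.05. The tests of H1–H4 are unaffected.

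**What to change.** Keep the product-specific label effects and show each with its 95% confidence interval. For each of the four outcomes, add one joint label-by-product interaction test (6 degrees of freedom) on the stacked data. Use the linear probability approach already chosen for moderation, so that the test is on the reported probability-difference scale. State how repeated responses are handled, for example by a participant random intercept or participant-clustered standard errors. Add one sentence: any statement that label effects differ by product will rest on this test, and otherwise the product results are descriptive.

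The cost is a sentence or two of text and four extra exploratory tests, with no new data. The downside is limited power, so the plan should also say that a non-significant result does not show that effects are equal across products.

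### The stated 80% power for an odds ratio of 1.16 does not follow from the plan's own inputs; at alpha 0.017 it is between about 23% and 68%

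*Combined protocol and SAP*

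**What the plan says.** The Sample Size and Power section of the combined protocol and SAP sizes the trial on "the 2 label designs that we anticipate will be most similar (i.e., the interpretative magnifying glass icon and interpretative text-only label"). Its inputs are:

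- a reference proportion: "Power analyses assumed 55% of participants in the interpretative magnifying glass icon" arm would answer correctly;
- "a two-tailed critical alpha of 0.017 (0.05 divided by 3 to correct for multiple comparisons");
- the conclusion that "a sample of 1,000 per condition (4,000 total) yields 80% power to detect effects of $OR=1.16$ or larger between any 2 label designs", a claim made for both co-primary outcomes and described as "equivalent to Cohen's $d=0.08".

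The same section adds: "This is a conservative estimate of effect size based on prior studies showing effect sizes of 1.10–1.80 between similar labels".

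Two other parts of the document bear on the calculation. Under Study Protocol, "These selection questions will be repeated 3 times, once for each food product", so each participant gives three answers per outcome. Under Main Analyses, the model is a mixed effects logistic regression with a random intercept, "accounting for repeated measures within participants", and label arm enters as indicator variables. The G*Power routine and the within-participant correlation are not given.

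**The concern.** With a proportion near one half, 1,000 people per arm and an alpha of 0.017, an odds ratio of 1.16 is a difference of only 3.7 percentage points (55% versus 51.3%). That looks too small to be detected with 80% power. Three answers per person help, but only to the extent that they are not correlated, and the plan's own model allows for correlation.

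The trial was sized on icon versus text-only, and H1 and H2 predict a full ranking of the labels. A reader who trusts the stated power would take a non-significant result on that contrast as fairly good evidence against a difference of 3.7 points. If the true power is a half or a third, the result does not support that reading.

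**Working it through.** **Inputs from the document.** p1 = 0.55; two-sided alpha = 0.017, so z = 2.387; 80% power, so z = 0.842; 1,000 participants per arm; 3 answers each; OR = 1.16.

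**Input not in the document.** The ICC. It is taken over its whole range, 0 to 1, with effective answers per arm n = 3,000 / (1 + 2 × ICC). ICC = 1 is equivalent to one answer per person.

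**Step 1: is the effect size self-consistent?** d = ln(1.16) × √3 / π = 0.082, which agrees with the plan's 0.08. So 1.16 is not a misprint; the power attached to it is the issue.

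**Step 2: second proportion.** The odds at 55% are 0.55/0.45 = 1.222. Dividing by 1.16 gives p2 = 0.5131; multiplying gives p2 = 0.5864. The downward case is shown below; the upward case gives power up to one percentage point lower.

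**Step 3: power.** Two-proportion normal approximation, pooled variance under the null:

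power = Φ{ [ |p1 − p2|√n − z × √(2p̄q̄) ] / √(p1q1 + p2q2) }

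with |p1 − p2| = 0.0369, √(2p̄q̄) = 0.7057 and √(p1q1 + p2q2) = 0.7052.

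- n = 1,000: (1.168 − 1.684) / 0.7052 = −0.732, so power is 23%.
- n = 3,000: (2.023 − 1.684) / 0.7052 = 0.481, so power is 68%.

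**Step 4: the range.**

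| ICC | Effective answers per arm | Power at OR 1.16, alpha 0.017 | OR detectable with 80% power | Power at OR 1.16 if alpha were 0.05 |
|---|---|---|---|---|
| 0 | 3,000 | 68% | 1.18 | 82% |
| 0.2 | 2,143 | 52% | 1.22 | 68% |
| 0.3 | 1,875 | 45% | 1.24 | 62% |
| 0.5 | 1,500 | 36% | 1.27 | 53% |
| 1 | 1,000 | 23% | 1.34 | 38% |

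**Step 5: answers needed.** n = (1.684 + 0.842 × 0.7052)² / 0.0369² gives about 3,800 independent answers per arm (about 3,860 in the upward direction). The design supplies at most 3,000. Setting 3,000 / (1 + 2 × ICC) = 3,803 gives an ICC of −0.11, which a random-intercept model cannot represent.

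**Step 6: where 1.16 might have come from.** Three calculations land close to it. None is the stated comparison, and the document does not show which, if any, was used.

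- Logistic regression with a standard-normal predictor and N = 2,000: exp[(2.387 + 0.842) / √(2,000 × 0.55 × 0.45)] = exp(0.145) = 1.156. That is an odds ratio per standard deviation of a continuous variable. A 1:1 arm indicator has a standard deviation of 0.5, so the same result corresponds to exp(0.290) = 1.34.
- A standardised difference with 3,000 independent answers per arm: d = 3.228 × √(2/3,000) = 0.083, which converts to exp(0.083 × π/√3) = 1.163. This ignores both the 55% and the correlation.
- Alpha 0.05 with ICC 0: detectable OR 1.156 to 1.157. The power statement uses 0.017.

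**Step 7: lower end of the cited prior range.** At OR 1.10, power at alpha 0.017 runs from 9% (ICC 1) to 29% (ICC 0).

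**The case against.** The strongest counter-argument is that 0.017 is not the alpha at which every contrast will be tested. Under Main Analyses, the three comparisons with the numerical label are unadjusted at 0.05. The three among interpretive labels use Bonferroni-Holm, so icon versus text-only could be tested at 0.05 if the other two reject. This stands as a description of the tests: the 23% to 68% range is the power at the stated alpha of 0.017, not the power of every contrast. It does not restore the figure. The plan attaches 80% to 0.017, and even at 0.05 power reaches 80% only when the ICC is about 0.02 or less.

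Second, if the standardised-difference route in step 6 was used, it matches both published figures (d 0.08, OR 1.16). The pure arithmetic gap is then 1.16 against 1.18, and the rest is an undisclosed ICC. That is possible, and it is why the size of the shortfall cannot be fixed from the document. But that route discards the plan's own 55% and assumes uncorrelated answers, while the analysis model allows for correlation.

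Third, the low end of the range needs ICC = 1, which is extreme, and any narrower range is an assumption. This is accepted; the full range is shown for that reason.

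Fourth, 1.16 lies near the bottom of the cited 1.10 to 1.80, and choosing the most similar pair is a cautious step. Also, icon versus text-only compares the labels predicted to rank second and third, so it does not by itself settle which design is best. Both points are fair. They temper the criticism of the word conservative and the stakes, but not the power figure.

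**Conclusion.** The concern holds. At two-sided alpha 0.017, with 55% in the icon arm, 1,000 per arm and three answers each, power for OR 1.16 is at most about 68% and may be as low as 23%. The odds ratio detectable with 80% power is 1.18 to 1.34. For an ICC of 0.2 to 0.5, which is an assumption, power is about 52% to 36% and the detectable odds ratio about 1.22 to 1.27. That the 80% is unattainable needs no assumption about the ICC beyond its lying between 0 and 1.

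These figures treat 1.16 as a marginal odds ratio and apply no loss. If 1.16 is meant as the mixed model's participant-specific odds ratio, power is lower still, at about 30% for an observed ICC near 0.22. It also falls if the 1,000 per arm is counted before the removals described under Exclusions and Outliers. None of this means that 4,000 participants are too few for larger differences between labels.

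**What to change.** Correct the power statement in Sample Size and Power:

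- Name the G*Power routine, and state the ICC with its basis.
- Replace OR 1.16 with the value that follows. For example: with 1,000 per condition, 3 answers per participant, 55% correct, two-sided alpha 0.017 and an assumed within-participant ICC of 0.2 to 0.5, the study has 80% power to detect a marginal odds ratio of about 1.22 to 1.27 (about 5 to 6 percentage points). The sponsor should substitute its own ICC if it has one.
- Restate Cohen's d to match: ln(1.22) × √3/π = 0.11 and ln(1.27) × √3/π = 0.13.
- Delete the word conservative where it describes the effect size, or add that effects near the lower prior bound of 1.10 are not powered.
- Say that 0.017 is the first Holm step, and that the comparisons with the numerical label are tested at 0.05.
- Say whether 1,000 per condition is counted before or after exclusions.

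The cost is a text change. No participants are added and no endpoint, model or testing rule changes; the plan claims a larger detectable effect than it does now.
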